8.2.3.2 Test of Attentional Performance for Children

The KiTAP is an automated computer-based assessment of attentional performance developed and normed for a pediatric population. The KiTAP is suitable for assessment of function in individuals of various ages, including children, adolescents, and adults, with FXS ([Knox et al 2012](#)). The task displays an “enchanted castle” animation and measures 8 aspects of attention: alertness, distractibility, flexibility, Go/NoGo, virtual scanning, vigilance, sustained attention, and divided attention. Only 4 of the 8 subtests will be administered in this study: alertness, distractibility, Go/NoGo, and flexibility.

The change from baseline in the KiTAP (for the 4 sub-tests presented in the CRF: alertness, distractibility, flexibility, Go/NoGo) and their corresponding parameters (mean, stddev, correct, omissions, anticipations for alertness; mean, stddev, correct, errors for flexibility, and mean, stddev, correct, errors, omissions for Go/NoGo parameters; distractor mean, distractor correct, distractor errors, distractor omissions, no distractor mean, no distractor correct, no distractor errors, no distractor omissions, total mean, total correct, total errors, total omissions for distractibility parameter) will be analyzed for Week 6 and Week 12, as described in [Section 8.1](#).

If value of some of KiTAP parameter is missing from the Baseline visit, the value from the Screening visit can be used for analysis. Missing data convention from the provider will be

used for missing assessments and scores. Otherwise, missing data from the assessment will be kept as missing.

[figure not shown]
8.2.3.3 Repeatable Battery for the Assessment of Neuropsychological Status

The RBANS provides a brief individually administered battery to assess cognitive function in individuals 12 years of age and older ([Randolph et al 1998](#)). The full battery consists of 12 subtests to assess immediate memory, visuospatial abilities, language, attention, and delayed memory. In this study, 6 subtests of the RBANS will be used: list learning (immediate memory), list recall (delayed memory), list recognition (delayed memory index), story memory (immediate memory index), story recall (delayed memory index), and picture naming (language index). Each subtest can be administered in 5 minutes or less.

Subtests total scores will be derived in the eCRF and analysis as described in [Section 8.1](#) will be used to analyze the change from baseline in the RBANS subset scores for Week 6 and Week 12.

If some subtest score of RBANS is missing from the Baseline visit, the subtest score from the Screening visit can be used for analysis. Missing data convention from the provider will be used for missing assessments and scores. Otherwise, missing data from the assessment will be kept as missing.

8.2.3.4 [REDACTED]

[REDACTED]

8.2.4 [REDACTED]

[REDACTED]

8.2.5 [REDACTED]

[REDACTED]

8.3. [REDACTED]

[REDACTED]

9. SAFETY ANALYSES

All safety data analyses will be conducted by using the Safety Set.

9.1. Adverse Events

9.1.1 Incidence of Adverse Events

An AE is defined as any untoward medical occurrence in a subject enrolled into this study regardless of its causal relationship to study drug. Subjects will be instructed to contact the investigator at any time after randomization if any symptoms develop.

A Treatment-Emergent Adverse Event (TEAE) is defined as any event AE not present before exposure to study drug or any event already present that worsens in either intensity or frequency after exposure to study drug and occurred within 30 days of last dose. TEAEs will be reported in tables regardless of seriousness.

For listings, any events after pre-specified range above will be flagged in the outputs.

The subject-incidence and event-incidence of TEAEs, TEAEs leading to study discontinuation, treatment-related TEAEs, serious TEAEs, severity of TEAEs, TEAEs with outcome of death, and seizure TEAEs will be summarized by treatment and overall. For summaries of severe or treatment-related AEs, for a given subject, the highest severity or relationship for a specific PT will be considered. Adverse events with missing start dates will be considered treatment emergent. All AEs will be coded using the most current Medical Dictionary for Drug Regulatory Affairs (MedDRA, version 20.1 or higher) and will be summarized by System Organ Class (SOC) and Preferred Term (PT). For each SOC and PT, a subject will be counted only once for subject-incidence tabulations. In addition, TEAE will be summarized by System Organ Class (SOC), High Level Group Term (HLGT), High Level Term (HLT), and Preferred Term (PT). For each SOC, HLT, and PT, a subject will be counted only once for subject-incidence tabulations. The Wilson 95% CIs will be displayed for the proportion of subjects experiencing TEAEs as a total across the 3 dosing regimens. Additional overall AEs (including non-TEAEs) by PTs will also be provided. Detailed listings of AEs, SAEs, treatment-related AEs, and TEAEs leading to study discontinuation will be provided.

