6.6.1.3 Eliciting and Documenting Adverse Events

Adverse events will be assessed beginning at enrollment (date of signed informed consent) and up to 30 days after the last dose of study drug, and must be followed until resolution or for 30 days after the subject's last study drug dose, whichever comes first.

Serious AEs that occur more than 30 days after the last dose of study drug need not be reported unless the investigator considers them related to study drug.

At every clinic visit after informed consent and at all phone visits (Table 6-1), subjects will be asked a standard nonleading question to elicit any medically related changes in their well-being. They will also be asked if they have been hospitalized, had any accidents, used any new medications, or changed concomitant medication regimens (both prescription and over-the-counter medications).

In addition to subject observations, AEs identified from any study data (eg, laboratory values, physical examination findings) or identified from the review of other documents (eg, subject diaries) that are relevant to subject safety or considered to be clinically significant, in the medical and scientific judgment of the investigator, will be documented on the AE page in the eCRF.

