14. APPENDICES

14.1. Imputation Algorithm for Partial and Missing Dates

Adverse Event, Concomitant Procedures and Concomitant Medications

- Partial/Missing Start Date
 - Missing day - Impute the 1st of the month unless month is same as month of first dose of study drug then impute first dose date
 - Missing day and month – impute 1st January unless year is the same as first dose date then impute first dose date
 - Completely missing – impute first dose date unless the end date suggests it could have started prior to this in which case impute the 1st January of the same year as the end date. When imputing a start date ensure that the new imputed date is sensible i.e. is prior to the end date of the AE or med.
- Partial/Missing End Date
 - Missing day - Impute the last day of the month unless month is same as month of last dose of study drug then impute last dose date
 - Missing day and month – impute 31st December unless year is the same as last dose date then impute last dose date
 - Completely Missing – need to look at whether the AE/medication is still ongoing before imputing a date and also when it started in relation to study drug. If the ongoing flag is checked then assume that AE is still present / medication is still being taken (i.e. do not impute a date). If the AE/medication has stopped and start date is prior to first dose date then impute the 1st dose date, if it started on or after first dose date then impute a date that is after the last dose date.

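### SAP 9.1.1 counts an adverse event with a missing start date as treatment emergent even when it ended before the first dose

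*SAP*

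**What the plan says.** SAP 9.1.1 defines a TEAE as "any event AE not present before exposure to study drug or any event already present that worsens in either intensity or frequency" after exposure, up to 30 days past the last dose. It then adds a rule for incomplete data: "Adverse events with missing start dates will be considered treatment emergent". Protocol 7.8.1 carries the same sentence. Neither place looks at the end date, and neither says whether a partly known start date counts as missing.

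SAP 14.1 gives its date algorithm under the title "Adverse Event, Concomitant Procedures and Concomitant Medications", so it covers AEs. For a completely missing start the instruction is to "impute first dose date unless the end date suggests it could have started prior to this". Where that exception applies, it is to "impute the 1st January of the same year as the end date". A further sentence asks that an imputed start be plausible, that is, earlier than the end date. Where only the year is known, the rule is to "impute 1st January unless year is the same as first dose date then impute first dose date".

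Protocol 6.6.1.3 starts AE collection at signed consent, and protocol 6.1.1 allows screening up to 21 days before Baseline. SAP 3.2.1 lists TEAEs, treatment-related TEAEs, TEAEs leading to study discontinuation and SAEs as the primary safety endpoints. SAP Section 12 declares one change from the protocol, the significance level for the age effect, and nothing on missing AE dates.

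**The concern.** Treating an undated event as treatment emergent is a sensible default when nothing else is known. Here something may be known. If the end date is before the first dose, the event cannot have begun or worsened after exposure, yet 9.1.1 still counts it. AEs are collected during screening, so such records can exist.

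The same record then receives a pre-dose start under 14.1. The SAP does not say which section sets the TEAE flag, or whether imputed dates are used for it at all. Two programmers could follow the SAP faithfully and produce different primary safety tables. There is also a knock-on effect: SAP 9.1.2 reports a TEAE with missing causality as related, so a screening event lacking both items would appear as a treatment-related TEAE.

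**Working it through.** **The plan's own precision figure.** SAP 4.2 gives a half-width of 13.9% for 6 events in 30 subjects, by Wilson's method. With z = 1.96, z² = 3.8415, p = 0.2 and n = 30:

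- denominator: 1 + z²/n = 1.1280
- centre: (p + z²/2n) / 1.1280 = (0.2 + 0.0640) / 1.1280 = 0.234
- half-width: z × √(p(1 − p)/n + z²/4n²) / 1.1280 = 1.96 × √(0.00533 + 0.00107) / 1.1280 = 0.139

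This gives 9.5% to 37.3%, as in SAP Table 2.

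**The two rules on test dates.** The start date is completely missing throughout. The narrow reading of 14.1 applies its exception only when the end date is before first dose. The literal reading applies it to any end date compatible with an earlier start.

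| First dose | AE end | SAP 9.1.1 | 14.1, narrow | 14.1, literal |
|---|---|---|---|---|
| 15 May 2019 | 10 May 2019 | TEAE | 1 Jan 2019, not TEAE | 1 Jan 2019, not TEAE |
| 5 Jan 2019 | 28 Dec 2018 | TEAE | 1 Jan 2018, not TEAE | 1 Jan 2018, not TEAE |
| 15 May 2019 | 20 May 2019 | TEAE | 15 May 2019, TEAE | 1 Jan 2019, not TEAE |
| 15 May 2019 | none | TEAE | 15 May 2019, TEAE | 15 May 2019, TEAE |
| 10 Dec 2018 | 20 Jan 2019 | TEAE | 10 Dec 2018, TEAE | 1 Jan 2019, TEAE |

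In the first two rows the sections disagree on either reading. That holds for every end date before first dose: 1 January of the end-date year cannot be later than the end date, so it also precedes first dose. In the third row they disagree only on the literal reading. In the last two rows they agree.

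**Size of one reclassified subject.** Assume the event is the subject's only TEAE.

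- Pooled, all 36 planned subjects treated: 1/36 = 2.8 points. For example, 6/36 = 16.7% (Wilson 7.9% to 31.9%) becomes 7/36 = 19.4% (9.8% to 35.0%).
- Pooled, on the Table 2 denominator: 1/30 = 3.3 points. 6/30 = 20.0% becomes 7/30 = 23.3% (11.8% to 40.9%), and the half-width goes from 13.9% to 14.6%.
- One arm of 36/3 = 12: 1/12 = 8.3 points. For example, 2/12 = 16.7% becomes 3/12 = 25.0%.

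If the subject has another TEAE, the overall subject incidence does not move. A system organ class or preferred term row moves only if the event is the subject's sole one in that row. Event counts move in every case.

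**The case against.** The best defence is that the two sections do different jobs. Section 9.1.1 is the only SAP text that sets TEAE status for a missing start date, and it repeats the protocol. Section 14.1 is a date appendix shared with medications and procedures, and it never mentions TEAEs. On that view 9.1.1 sets the flag and 14.1 fills in dates. This is a fair inference, but the SAP does not state it, and it leaves the over-count of pre-dose events untouched.

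It can also be said that over-counting is the cautious direction for a safety endpoint and that the cases will be rare. Protocol 6.6.1.4 collects time of onset and does not treat a stable condition already present at screening as an AE. Screening is short, and protocol 8.1 promises full source data verification. The SAP also provides an AE summary that includes non-TEAEs, as well as listings, so no event disappears. All of this stands, and it limits the size of the problem. An event that ended before dosing is also unlikely to appear as a TEAE leading to discontinuation.

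A reader might go further and infer that the two rules are opposed for missing dates in general, or that 14.1 strips out on-treatment events that may be drug related. The documents do not support either. The default in 14.1 is the first dose date, which gives the same class as 9.1.1, and a start year equal to the dosing year leads there too. Loss of on-treatment events needs the literal reading, which would leave the default almost nothing to cover except events without an end date. The plausibility sentence favours the narrow reading, because the exception is needed where imputing the first dose date would put the start after the end. The trigger is still loose enough to be misprogrammed.

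**Conclusion.** The point holds in a limited form. As written, 9.1.1 and protocol 7.8.1 give a wrong class to one kind of record: an AE with a missing start date whose end date is before first dose. The error is an over-count in a primary safety endpoint, and it conflicts with 9.1.1's own definition and with 14.1 on either reading. Under-counting through 14.1 is only a possibility created by its wording.

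The per-subject shifts above are ceilings. They assume the event is the subject's sole TEAE, that all 36 estimated subjects are treated (for the 2.8 points) and that arms are equal (for the 8.3 points). The documents do not show how many such records will occur; few are likely. Table 2's stated precision is barely affected. The reason to act is that the class of a primary-endpoint event should not depend on which SAP section is programmed.

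**What to change.** Make four small changes before database lock:

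1. In SAP 9.1.1, state that an AE with a completely missing start date is treatment emergent unless its end date is before the first dose date. Say in the same place how partly known start dates are flagged.
2. In SAP 14.1, limit the 1 January imputation to end dates before first dose, and impute the first dose date in all other cases. Let the plausibility check accept an imputed start on the end date itself, so that an event ending on Day 1 is covered.
3. State that 9.1.1 governs the TEAE flag.
4. List the departure from protocol 7.8.1 in SAP Section 12, and check it against protocol 7.8, which requires an amendment for major changes to endpoint definitions or analyses.

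The logic is already in the plan. For a medication with no start date, SAP 7.1 uses the stop date: before the dose date means not concomitant, on or after it means concomitant. The cost is about one sentence in each place and one date comparison in the program. No new data are needed.

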9.1.2 Relationship of Adverse Events to Study Drug

A TEAE is considered treatment-related if there is any causal relationship between the study medication. If the relationship of a TEAE is missing or the TEAE is possibly or probably related, the TEAE is reported as related. The number and percentage of subjects experiencing treatment-related TEAEs and number of events will be summarized.

9.1.3 Severity of TEAEs

A summary of TEAEs by severity will be presented in a table. The severity that will be presented represents the most extreme severity captured on the eCRF page. The possible severities are 'Mild,' 'Moderate,' and 'Severe'. In the TEAE severity table, if a subject reported multiple occurrences of the same TEAE, only the most severe TEAE is presented. TEAEs that are missing severity will be presented in tables as 'Severe' but will be presented in the data listing with a missing severity.

9.1.4 Serious TEAEs

A serious treatment-emergent adverse event is any untoward medical occurrence that, at any dose, results in death, life-threatening, requires hospitalization or prolongation of existing hospitalization, hospitalization for elective treatment of a pre-existing condition that did not worsen from baseline is not considered an AE, results in disability/incapacity, and congenital anomaly/birth defect.

Serious TEAEs will be categorized and presented by SOC and PT in the same manner to that described in [Section 9.1.1](#).

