6.6.1.2 Serious Adverse Events

An SAE is defined as any event that meets one of the following criteria:

- Results in death
- Is immediately life threatening
- Requires inpatient hospitalization or prolongation of existing hospitalization
- Results in persistent or significant disability/incapacity not consistent with baseline level
- Is a congenital anomaly/birth defect

Important medical events that may not result in death, be life threatening, or require hospitalization may be considered SAEs when, based upon appropriate medical judgment, they may jeopardize the subject or may require medical or surgical intervention to prevent one of the outcomes listed in this definition. Examples of such medical events include allergic bronchospasm requiring intensive treatment in an emergency room or at home, blood dyscrasias or convulsions that do not result in inpatient hospitalization, or the development of drug dependency or drug abuse.

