6.6.1.4 Reporting Adverse Events

All AEs reported or observed during the study will be recorded on the AE page in the eCRF. Information to be collected includes the following:

- Drug treatment
- Dose

- Event term (diagnosis, not symptoms)
- Time of onset
- Investigator-specified assessment of severity and relationship to study drug
- Time of resolution of the event
- Seriousness
- Any required treatment or evaluations
- Outcome

Adverse events resulting from concurrent illnesses, reactions to concurrent illnesses, reactions to concurrent medications, or progression of disease states must also be reported. All AEs will be followed to adequate resolution. The Medical Dictionary for Regulatory Activities (MedDRA) will be used to code all AEs.

Any medical condition that is present at the time that the subject is screened but does not deteriorate should not be reported as an AE. However, if it deteriorates at any time during the study, it should be recorded as an AE.

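### SAP 9.1.4 lists the criteria for a serious TEAE without the protocol's important-medical-event criterion, and SAP 12 does not declare the difference

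*SAP*

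**What the plan says.** SAP 9.1.4 defines a serious TEAE as "any untoward medical occurrence that, at any dose, results in death, life-threatening, requires hospitalization or prolongation of existing hospitalization". The same sentence continues with "hospitalization for elective treatment of a pre-existing condition that did not worsen from baseline is not considered an AE, results in disability/incapacity" and closes with congenital anomaly or birth defect. The only other instruction in the section is to present serious TEAEs by SOC and PT in the manner of SAP 9.1.1. It refers neither to the protocol's SAE definition nor to an eCRF field.

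Protocol 6.6.1.2 lists five criteria: death, threat to life, hospitalization, disability and congenital anomaly. It then adds a sixth route: "Important medical events that may not result in death, be life threatening, or require hospitalization may be considered SAEs when" medical judgment finds that they may endanger the subject or call for intervention to prevent a listed outcome. Its examples include "blood dyscrasias or convulsions that do not result in inpatient hospitalization".

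Five other places bear on the point:

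- Protocol 6.6.1.4 names seriousness among the items recorded for every AE in the eCRF, and protocol 6.6.1.5 has sites enter SAEs against the criteria of 6.6.1.2.
- Protocol 7.1 and SAP 3.2.1 both name SAEs as a primary safety endpoint.
- SAP 1 undertakes to identify considerations that differ substantially from the protocol.
- SAP 12 declares one change only, the significance level for the age effect in the MMRM.
- Protocol 7.8 lets the SAP modify the protocol's plans, but says that major changes to endpoint definitions will also go into a protocol amendment.

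**The concern.** Investigators classify events under one definition, and the section that governs the summary table states another. The SAP list leaves out a whole route to seriousness, and the protocol's own example of that route, a convulsion managed without admission, matters in this programme. Protocol 1.4 reports two subjects with an SAE of seizure in the earlier Angelman study, and the SAP gives seizure TEAEs a table of their own.

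At stake is whether the serious-TEAE table, which summarizes a primary safety endpoint, agrees with the SAEs that sites reported. If a programmer follows the SAP text, the table and the SAE listing can disagree, and nothing in the SAP would warn the reader.

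**Working it through.** No arithmetic applies. The check sets the two definitions side by side and then follows one event through the plan.

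**Side by side**

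| Criterion | Protocol 6.6.1.2 | SAP 9.1.4 |
|---|---|---|
| Death | present | present |
| Threat to life | "Is immediately life threatening" | present, without the word for immediacy |
| Hospitalization | "Requires inpatient hospitalization or prolongation of existing hospitalization" | present, without the restriction to inpatient stays |
| Disability | "Results in persistent or significant disability/incapacity not consistent with baseline level" | present, without the qualifiers on persistence, significance and baseline level |
| Congenital anomaly | present | present |
| Important medical events | present, with examples | **absent** |
| Elective treatment of a stable pre-existing condition | not mentioned | stated not to be an AE |

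**Which differences can reach the table**

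1. *Important medical events.* Take a convulsion after first dose that needs no admission, is not life threatening and leaves no disability, but that the investigator judges an important medical event. Under protocol 6.6.1.2 it is an SAE. Under protocol 6.6.1.4 and 6.6.1.5 the site records it as serious. It meets none of the criteria in SAP 9.1.4. The outputs then depend on how the table is built:
   - With the SAP list applied literally, the event is in the SAE listing (SAP 9.1.1, if that listing follows the site's classification) and in the seizure table (SAP 9.1.7), but not in the serious-TEAE table.
   - With the eCRF seriousness field, it is in all three.
   - An important medical event that is not a seizure, such as the protocol's blood dyscrasia example, has no separate table to fall back on.

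2. *Dropped qualifiers.* Taken alone they make the SAP list broader. They could add an event only if someone re-screened AEs that the site had called non-serious, and the SAP describes no such step. The protocol's own paragraph on important medical events also refers to threat to life and hospitalization without the first two qualifiers. These omissions have no clear route to the count.

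3. *Elective-treatment clause.* It says such a hospitalization is not an AE at all, so read literally it bears on every AE count and not on seriousness alone. Protocol 6.6.1.4 already says that a condition "present at the time that the subject is screened but does not deteriorate should not be reported as an AE". That rule does not mention hospitalization, but the overlap is large and little should change.

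**Declared or not.** SAP 12 contains one entry, on the MMRM age effect. None of the rows above is declared.

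**The case against.** The strongest reply is that SAP 9.1.4 is a loose paraphrase and not a derivation rule. Its grammar is broken and it names no data source. The neighbouring sections 9.1.2 and 9.1.3, by contrast, give operational rules that cover missing values. Whether something is an important medical event is a medical judgment that a programmer cannot re-derive, so the natural source is the eCRF field. SAP 3.2.1 names SAEs without redefining them. The current protocol keeps important medical events, which suggests that no redefinition was intended. SAP 1 speaks of statistical considerations that differ substantially, and it is arguable whether a seriousness definition is one. The Wilson interval planned in SAP 9.1.1 is for all TEAEs, so it would not move.

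Most of this stands as a reason to expect a small effect. It does not repair the text. SAP 9.1.3 ties severity to the eCRF page, whereas 9.1.4 gives a definition and no field. The likely practice is therefore an inference, and the written rule points the other way.

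A reader might go further in three ways that the documents do not support:

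- One might count every wording difference as a separate way to alter the result. Only the omission of important medical events has a plausible route to the table.
- One might conclude that the sponsor has redefined a primary endpoint. Nothing shows that intent, and protocol 7.8 would have called for an amendment if the change were major.
- One might conclude that SAEs will go unreported. Sites report under protocol 6.6.1.2, SAEs are listed, and seizure TEAEs are tabulated separately.

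**Conclusion.** The point holds and is minor: the rule is wrong as written. SAP 9.1.4 omits a criterion that protocol 6.6.1.2 includes, for an endpoint that both documents call primary, and SAP 12 does not say so.

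The harm depends on one assumption, that the serious-TEAE table is programmed from the SAP list and not from the eCRF seriousness field. The SAP does not settle which. Under the first, SAEs that qualify only as important medical events leave the table. Under the second, none do. The documents give no rate for such events, so the size cannot be estimated, and it is probably small. The overall TEAE count and its confidence interval do not depend on how important medical events are classified. The elective-treatment clause and the dropped qualifiers are secondary.

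**What to change.** Replace the list in SAP 9.1.4 with one sentence: a serious TEAE is a TEAE recorded as serious in the eCRF seriousness field per protocol 6.6.1.2, including important medical events. This also removes the elective-treatment clause and the dropped qualifiers as sources of doubt.

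If a narrower definition is intended, declare and justify it in SAP 12 and, since protocol 7.8 asks this for major changes to endpoint definitions, put it in a protocol amendment.

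The first option costs one sentence. It needs no new data and no new table, because seriousness is already collected for each AE. The second costs an entry in SAP 12 and an amendment.
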